7.2 Data handling

7.2.1 Calculation of time-to-event

In the following definitions the time of study entry has been defined as date of first dose of study medication (taken from the dosage administration record on the CRF).

The date of last contact (used in the censoring rules below) is collected on the End of Study/Survival Information page of the CRF. However, it should be noted that it is only planned for contact with patients to take place at the clinic visits and so the date of last contact captured on the CRF should always be equal to the date of last visit attended.

Progression Free Survival:

PFS is defined as the time from date of first dose of study medication until the date of the first documented disease progression or death due to any cause. Date of progression and date of death will be captured on the CRF.

For the purpose of calculating the PFS Rate if a patient has not progressed or died at the date of analysis cut-off, or when he/she received further anticancer therapy, then their time to progression or death will be censored at the time of last tumor assessment, before the first cut-off date or the anticancer therapy date.

Progression Free Survival Rate:

The PFS rate is defined as the survival function at the end of the time point based on a Kaplan-Meier analysis of the time to either progression (as per the local radiological review) or death (see next section for handling of censored data).

The time points at which PFS rate will be summarized are: 8 weeks, 20 weeks, 32 weeks, 44 weeks, 56 weeks and every 12 weeks thereafter as appropriate.

Overall Survival:

Overall survival is defined as the time from date of first dose of study medication until death due to any cause. The date of death will be captured on the CRF.

If a patient is still alive and not lost to follow-up at the end of the study then their time to death will be censored at the date of last contact date, as recorded on the CRF.

If the patient has been lost to follow-up by the end of the study then their time to death will be censored at the date of last contact as recorded on the CRF.

In the event that a date of last contact has not been recorded on the CRF, then the date of the last assessment recorded should be used instead.

Duration of Response:

The duration of response (CR or PR) is defined as the time from the first occurrence of PR or CR (as per the local radiological review) until the date of the first documented disease progression or death due to underlying cancer. If a patient has not had an event, duration of response is censored at the date of last adequate tumor assessment prior to starting new anticancer therapy.

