3.1 Assessments

Upon provision of written, informed consent patients will be given a unique 9 digit patient number. This will be a combination of their 4 digit center number and 5 digit subject number.

The patient will be assessed for their eligibility to take part in the study (i.e. receive study medication) using the inclusion and exclusion criteria stated in the protocol (Sections 5.1 and 5.2). If the patient fails to start on treatment for any reason, this reason will be entered on the Screening Log. No data for screen failures will be entered into the clinical database.

Patients who are eligible for treatment will be dispensed their study medication on completion of their baseline visit. Patients should present to the clinic on Day 1 and Day 15 of treatment Cycles 1, 2, and 3 and Day 1 of each subsequent treatment cycle to complete the assessments detailed in Table 6 of the protocol, until completion of treatment which will occur when the patient experiences disease progression, unacceptable toxicity, death or discontinues from the study for any other reason. An end of study treatment assessment should then be performed. All patients will have a follow-up visit 28 days after the last dose of the study drug to follow for adverse events (AEs) and serious adverse events (SAEs) that may have occurred after discontinuation from the study.

Tumor response will be assessed at 8 weeks (+/- 1 week), and every 12 weeks (+/- 1 week) thereafter until determination of disease progression and at the end of the study.

Patients who discontinue treatment, or are withdrawn from treatment by the investigator, for any reason, should complete an early discontinuation assessment. All patients who discontinue treatment will continue to have tumor assessments at 12-week intervals until the initiation of new cancer therapy.

The efficacy assessments for this study will be the assessment of tumor response/progression and survival status. Tumor response/progression assessments should be performed by a Computerized Tomography (CT) or Magnetic Resonance Imaging (MRI) scan. The same imaging modality used at screening must be used for all subsequent follow-up assessments.

Safety assessments will consist of evaluating AEs and SAEs, laboratory parameters including hematology, chemistry, vital signs and documentation of all concomitant medications and/or therapies. The Karnofsky Performance Status score will also be recorded.

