3.5 Sample size calculation

The sample size for this study was determined with reference to estimating a CI for the PFS rate at 10 months, assuming (for simplicity) the use of the normal approximation to the binomial distribution and assuming that a CI for a proportion is based on this normal approximation. To be able to estimate a 95% CI for the PFS rate, centered at 0.50, and having an expected total interval width of approximately 0.27, requires a sample size of 55 patients in each of the 2 cohorts (first- and second-line). With 95% confidence, the expected total interval width is approximately 0.19 for all 110 patients (both cohorts combined).

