YYYY	If the year part is the same as the year of first dose of study medication, impute with the date of first dose of study medication. Otherwise, impute with the 1st of January of the known year.	YYYY	Impute as 31'st December of the known year.
YYYY-MM	If the known part is same as the date of first dose of study medication then impute with date of first dose of study medication. Otherwise, impute with the 1st of the known month.	YYYY-MM	Impute as the last day of the known month.
All missing	If the known end date is after date of first dose of study medication then impute with the date of first dose of study medication. Otherwise, impute with the date of informed consent.	All missing	Impute as date of last contact

Disease Progression:

If disease progression or death is documented after one single missing tumor assessment, the actual event date of disease progression/death will be used for the PFS event date. If disease progression is documented after two or more missing tumor assessments, the PFS time of the patient will be censored at the date of the last tumor assessment with overall lesion response of CR, PR or SD.

Additional sensitivity analyses will be performed where:

1. The actual event date of disease progression/death will be used for the PFS event date, irrespective of whether it is preceded by missing tumor assessments;
2. In case of a documented progression/death after one or more missing tumor assessments, disease progression is considered to have occurred at the next scheduled tumor assessment after the date of the last tumor assessment with overall lesion response of CR, PR, or SD.

Duration of Response:

The same rules for missing data for calculation of duration of response will be applied as for PFS described above.

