8.6 Dosage Administration and Compliance

Study medication, RAD001, is given as a 10mg oral dose to be taken daily until the end of treatment. The dose administered throughout the entire treatment period should be captured on the CRF, including any changes in dosing initiated by the investigator for patients unable to tolerate the planned dosage, and any changes as a result of lack of compliance with the planned dosing regimen by the patient.

The total duration of treatment will be calculated as the number of days from the first to the last dose of study medication inclusive (regardless of any breaks in treatment). The total duration of treatment will also be categorized as up to 4 months, >4 to 8 months, >8 to 12 months, >12 to 16 months, >16 to 20 months, >20 to 24 months and >24 months. This will be calculated by dividing the duration of treatment in days by 365.25/12. The duration in days will be summarized and the number of patients in each 4-month treatment category will also be presented.

All dosage administration data will also be listed.

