	No recurrence	xx (xx.x%)
Lost to follow-up	Overall	xx (xx.x%)
	Already experienced recurrence	xx (xx.x%)
	No recurrence	xx (xx.x%)

Percentages are based on the number of patients in ITT population.
 With recurrence refers to subjects that had disease progression prior to death.
 Source: Listings 16.6-1.2 and 16.6-1.4

Table 14.6-2.1 (page 1 of 1)
Analysis of Progression Free Survival Rate
Population ITT

	First-line Patients N = xxxx	Second-line Patients N = xxxx	Total N = xxxx
PFS Events	xxx	xxx	xxx
PFS Rate	xx.xx	xx.xx	xx.xx
95% CI for PFS Rate	(xx.xxx, xx.xxx)	(xx.xxx, xx.xxx)	(xx.xxx, xx.xxx)

Number of patients achieving PFS = number of subject that experienced progression or died prior to the time of data analysis cut-off.

PFS Rate = survival function at the time of data analysis cut-off based on a Kaplan-Meier analysis of time to either progression or death.

The 95% CI also comes from the Kaplan-Meier analysis.

Source: Listings 16.6-1.5

Table 14.6-2.2 (page 1 of 1)
 Analysis of Progression Free Survival Rate - Sensitivity Analysis
 Population ITT

	First-line Patients N = xxxx	Second-line Patients N = xxxx	Total N = xxxx
Sensitivity Analysis 1:			
PFS Events	xxx	xxx	xxx
PFS Rate	xx.xx	xx.xx	xx.xx
95% CI for PFS Rate	(xx.xxx, xx.xxx)	(xx.xxx, xx.xxx)	(xx.xxx, xx.xxx)
Sensitivity Analysis 2:			
PFS Events	xxx	xxx	xxx
PFS Rate	xx.xx	xx.xx	xx.xx
95% CI for PFS Rate	(xx.xxx, xx.xxx)	(xx.xxx, xx.xxx)	(xx.xxx, xx.xxx)

Number of patients achieving PFS = number of subject that experienced progression or died prior to the time of data analysis cut-off.

PFS Rate = survival function at the time of data analysis cut-off based on a Kaplan-Meier analysis of time to either progression or death.

The 95% CI also comes from the Kaplan-Meier analysis.

Sensitivity Analysis 1 = Actual event date of disease progression/death used for the PFS event date, regardless of whether is it proceeded by missing tumor assessments.

Sensitivity Analysis 2 = In case of a documented progression/death after one of more missing tumor assessments, disease progression is considered to have occurred at the next scheduled tumor assessment after the date of last tumor assessment with overall lesion response of CR, PR, or SD.

Source: Listings 16.6-1.5

Table 14.6-2.3 (page 1 of 2)
 Progression Free Survival Descriptive Statistics
 Population ITT

Time to Event	Censored *	Event #	Product Limit Estimates			
			Survival Rate	95% CI of Survival Rate	Failure Rate	Survival Standard Error

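### The week-by-week PFS rates are read on the nominal scan day, so progressions found at permitted late scans drop out of that scan's row

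*SAP*

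**What the plan says.** The primary objective is the PFS rate over time (SAP 2.1). SAP 7.2.1 defines the rate this way: "The PFS rate is defined as the survival function at the end of the time point", from a Kaplan-Meier analysis. It then lists the read-off times: "The time points at which PFS rate will be summarized are: 8 weeks, 20 weeks, 32 weeks, 44 weeks, 56 weeks", continuing every 12 weeks.

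Those times coincide with the scan schedule in SAP 3.1: "Tumor response will be assessed at 8 weeks (+/- 1 week), and every 12 weeks (+/- 1 week) thereafter". Protocol 7.5.1 has the same window and keeps later scans on the original grid after a delayed or unscheduled one, so every read-off time falls in the middle of a scan window. SAP 7.1 applies no visit windowing, and progression takes its documented date. The shells of Tables 14.6-2.3 and 14.6-2.4 have rows cut at ≤ Week 8, ≤ Week 20 and so on, each counting the progressions and deaths in its period.

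No formula turns PFS dates into days. The one explicit day count is for treatment duration (SAP 8.6): "calculated as the number of days from the first to the last dose of study medication inclusive".

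Tables 14.6-2.1 and 14.6-2.2 use another reading time ("PFS Rate = survival function at the time of data analysis cut-off") and are not affected by this point.

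**The concern.** Reading the curve on the nominal day splits each scan's findings in two. Patients scanned early or on the day count in that scan's row. Patients scanned within the window but after the nominal day count only in the next row, 12 weeks later. The row then depends partly on how late sites scan, and the shift goes one way: the stated rate is too favourable as a description of that week.

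Sensitivity analysis 2 does not correct this. It re-dates progressions only under one condition: "In case of a documented progression/death after one or more missing tumor assessments". A late scan inside the window is not a missing one.

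The missing day-count rule makes it worse. If PFS were counted inclusively, as treatment duration is, a scan exactly on schedule at Visit 6 (Cycle 3 Day 1, two 28-day cycles after first dose) would have a PFS time of 57 days and miss the week-8 row. Two programmers could produce different tables from the same data.

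**Working it through.** **1. The plan's own precision.** SAP 3.5 sizes the trial by "estimating a CI for the PFS rate at 10 months", with the interval centred at 0.50. The width is 2 × 1.96 × √(0.25/n):
- n = 55: 0.264 (plan: about 0.27)
- n = 110: 0.187 (plan: about 0.19)

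Both agree. The half-widths are about 13 points per cohort and 9 points overall. Week 44 is 308/30.4375 = 10.1 months, so it is the row nearest the design landmark.

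**2. Model.** The documents give no scan-date distribution, so the following are assumptions.
- True progression is exponential with a 10-month median, to match the design's 0.50 at 10 months: λ = ln 2/304.375 = 0.002277 per day.
- Scans fall at day 56 + 84k plus a whole-day offset within ±7.
- Progression is dated at the first scan on or after onset.
- A share q of events is dated exactly (deaths, unscheduled scans). There is no censoring.

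The true proportions exp(−λt) are 0.880 at day 56, 0.727 at day 140 and 0.496 at day 308.

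**3. Week-8 row by hand, PFS as a date difference, q = 0.** With offsets uniform on −7 to +7, 8 of 15 scans fall on or before day 56, on average at day 52.5. The share with detected progression is 8/15 × (1 − exp(−0.002277 × 52.5)) = 0.533 × 0.1127 = 0.060. The row reads 0.940 against a true 0.880, an excess of 6.0 points. The excess scales with 1 − q.

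**4. Weeks 8, 20 and 44, q from 0 to 30%.**

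| Scan dates | Excess, date difference | Excess, inclusive count (+1 day) |
|---|---|---|
| Uniform over ±7 days | +3.6 to +7.5 points | +4.1 to +8.5 points |
| Half on the nominal day, half uniform | +1.8 to +3.7 points | +5.7 to +11.9 points |
| All on the nominal day | 0 | +7.4 to +15.3 points |
| Uniform, −7 to 0 | up to +0.7 points | – |

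For half on the day and q = 15%, the rows read 0.906, 0.759 and 0.518 against 0.880, 0.727 and 0.496. If every scan were 1 to 7 days late (q = 0, date difference), week 44 would read 0.595 against 0.496.

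The 15.3 arises at week 20. With all scans on the day and an inclusive count, that row contains only the week-8 scan's findings: 0.880 − 0.727 = 0.153.

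**5. A shorter median gives more.** At 5 months with a date difference, the excess is +1.9 to +5.9 points (half on the day) and +3.9 to +11.9 points (uniform).

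**6. Reading seven days later, date difference.** The row is within 0.4 point of the true nominal-week proportion in the uniform, half-on-day and all-on-day settings. It is within 0.7 point if all scans are early, and 0.7 point low at week 8 if all are late (0.873 against 0.880).

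**The case against.** The strongest reply is that PFS is defined by documented progression, so the Kaplan-Meier value at day 56 is the right estimate of what the plan defines. The rows are time rows, not visit rows. A day-59 progression is not lost; it counts on its own date and appears in the next row. Detection lag is a feature of any scan-based PFS. This stands as far as it goes: the estimator is sound, and the curve, the median and its interval do not change. But the read-off times were set on the scan weeks, and a row that omits part of its own scan's findings, by an amount set by site punctuality, is a poor report of the primary objective.

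The reference to the end of the time point in SAP 7.2.1 could mean the end of the window. It is undefined, though, and the shells cut at the nominal week.

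The size is also open to challenge. The inclusive-count figures need a rule that the SAP states only for treatment duration, and Listing 16.6-1.5 (days from treatment start to progression) fits a date difference at least as well. Protocol 7.5.1 asks for immediate imaging on suspected clinical progression, so the exactly dated share could exceed 30%. At 50%, with half the scans on the day, the excess falls to about 1.3 to 1.9 points (half of the q = 0 values, 2.5 to 3.7). Both points are fair. They narrow the range without removing the dependence on scan timing.

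**Conclusion.** The concern holds. As written, the rows of Tables 14.6-2.3 and 14.6-2.4 depend on how late sites scan and on an unstated one-day convention.

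Under the assumptions above and a date difference, the excess is about 2 to 7 points when some scans are late, against a planned half-width of about 9 points overall. It is at most 0.7 points when none are late. An inclusive count could add more than the overall half-width. These figures rest on assumed scan dates, an exponential curve, a 10-month median and no censoring. More deaths or unscheduled scans shrink them; a shorter median enlarges them.

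No hypothesis test or success threshold depends on these rows. The fault lies in what a row means, so it should be fixed, but it does not undermine the analysis as a whole.

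**What to change.** In SAP 7.2.1 and the shells of Tables 14.6-2.3 and 14.6-2.4:

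- Read the Kaplan-Meier curve at the close of each scan window: weeks 9, 21, 33, 45, 57 and every 12 weeks thereafter (days 63, 147, 231, 315, 399 after first dose).
- Label each row by its scan (week-8 scan, week-20 scan and so on).
- State the rule: PFS days = event or censoring date minus date of first dose. If one day is added, move the cut-points to days 64, 148, 232, 316 and 400.
- Leave Tables 14.6-2.1 and 14.6-2.2 as they are on this point.

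The cost is two sentences and new cut-points in two shells; no new data are needed. The reported rates may become a few points less favourable. Each row will include deaths and unscheduled progressions from the extra week, and scans later than the window will still be missed. The row nearest the design landmark moves from 10.1 to 10.35 months (315/30.4375).

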10.5.1.2 Objective Response Rate and Duration

The overall tumor response will be based on the data as per local radiological review, following RECIST criteria. The ORR is defined as the proportion of patients with CR or PR. The ORR (CR + PR) will be summarized in terms of percentage with 95% CIs.

The duration of overall response (CR or PR) will also be calculated, and is defined as the time from the first occurrence of PR or CR (as per local radiological review) until the date of the first documented disease progression or death due to underlying cancer. If a patient has not had an event, or when he/she receives any further anticancer therapy, duration of overall response is censored at the date of the last adequate tumor assessment. In case of missing data, the same rules will be applied as for PFS (see [Section 10.4.3](#)).

Duration-of-response curves (graphing the proportion of patients remaining free from progression and death due to cancer) will be displayed, overall and by strata, according to the Kaplan-Meier product-limit method, for those patients who had an overall response. This proportion over time will also be tabulated. The resulting median duration of response will be given with 95% CIs.

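### The SAP's duration-of-response rule leaves out the protocol's separate censoring trigger for new anticancer therapy, so a cancer death after a switch can count as an event

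*SAP*

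**What the plan says.** **Protocol 10.5.1.2** gives two grounds for censoring: "If a patient has not had an event, or when he/she receives any further anticancer therapy, duration of overall response is censored". The censoring date is the last adequate tumor assessment.

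**SAP 7.2.1, Duration of Response**, gives one: "If a patient has not had an event, duration of response is censored at the date of last adequate tumor assessment". The sentence goes on to tie that date to new therapy: "duration of response is censored at the date of last adequate tumor assessment prior to starting new anticancer therapy". The event runs "until the date of the first documented disease progression or death due to underlying cancer", with no requirement that it precede new therapy.

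**SAP 7.2.1, Progression Free Survival**, keeps new therapy as its own ground: "or when he/she received further anticancer therapy, then their time to progression or death will be censored at the time of last tumor assessment".

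**SAP 7.2.3** adds: "The same rules for missing data for calculation of duration of response will be applied as for PFS described above". Under those PFS rules, progression or death after a single missed assessment keeps its actual date. Progression after two or more missed assessments is censored at the last assessment showing CR, PR or SD.

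**The concern.** In the SAP sentence, new therapy acts only once a patient is known to have had no event. A responder who stops RAD001 without progression, starts another drug and later dies of cancer has had an event as the SAP defines it, so the censoring clause is never reached. The protocol would censor that patient.

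The case can arise. Treatment may end for toxicity without progression (Protocol 6.6.5), new therapies are recorded up to data cut-off (Protocol section 4), and survival information is sought after discontinuation (Protocol 6.6.6.1). Scheduled scans stop at the switch, so the later event would most likely be a death.

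At stake is whether duration of response follows the protocol and agrees with PFS in the same patient. As worded, two programmers could take the same data and report different results.

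**Working it through.** No figure in the plan rests on this rule, so the check is a comparison of wording, a worked patient and two illustrative simulations.

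**1. Worked patient (assumed dates on the planned scan schedule of weeks 8, 20, 32, 44, 56).** First PR at week 8, last adequate scan still in response at week 32, new therapy at week 34, no progression before the switch.

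| Rule | Cancer death at week 38 | Cancer death at week 80 |
|---|---|---|
| Protocol 10.5.1.2 | censored, 32 − 8 = 24 weeks | censored, 24 weeks |
| SAP 7.2.1 read literally | event, 38 − 8 = 30 weeks | event, 80 − 8 = 72 weeks |
| SAP PFS, same patient | censored at week 32 | censored at week 32 |

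In the second case the response (72 weeks) outlasts the patient's observed PFS time (32 weeks).

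**2. Does the missed-assessment rule close the gap?** Not clearly. Its two-or-more clause names progression, not death, and scans after a switch are not scheduled, so it is arguable that none is missing. Even if the clause were stretched to deaths and to unscheduled scans, the death at week 38 falls before the next nominal scan at week 44. Nothing has been missed, and the event stands at 30 weeks.

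**3. Direction of the effect.** Under the literal reading, a responder who switches and dies of cancer before cut-off is followed to death. One who switches and survives is censored back at the last scan before the switch. Follow-up after the switch is therefore kept only for those who die. One patient's record lengthens, but the estimate gains events and no matching event-free time.

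**4. Simulation A.** All inputs are assumptions: 35 responders (for scale, 110 patients × the 32% response rate cited in Protocol 1.2.3.4 = 35), exponential duration with median 8 months, switch at a random point of the patient's own duration, cut-off uniform on 8 to 26 months, 3,000 repeats. Change in the typical Kaplan-Meier median (months), literal SAP minus protocol:

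| Share switching | Median switch to cancer death: 2 | 6 | 12 | 18 months |
|---|---|---|---|---|
| 5% | −0.42 | −0.16 | −0.01 | −0.03 |
| 10% | −0.78 | −0.30 | −0.11 | −0.02 |
| 20% | −1.72 | −0.76 | −0.41 | −0.28 |

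The protocol-rule median in these runs is 8.2 to 9.3 months against the 8 assumed, because the switch time depends on the patient's own duration. The table shows the difference between the rules, not which is nearer the truth.

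**5. Simulation B.** Assumptions: exponential duration with median 43.5 weeks, scans every 12 weeks from response, switch assigned uniformly at 12 to 40 weeks after response in the stated share, exponential time to cancer death after the switch with median 52 weeks, cut-off uniform on 44 to 122 weeks after response.

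| Share assigned a switch | Responders with a different outcome | Of 35 | Kaplan-Meier change at 48 weeks | at 84 weeks |
|---|---|---|---|---|
| 10% | about 4% | 1 | −0.6 points | −1.5 points |
| 20% | about 8% | 3 | −1.2 points | −3.1 points |
| 30% | about 11% | 4 | −1.8 points | −4.7 points |

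The affected records lengthen by 33 weeks on average. The median does not move. With post-switch median survival varied from 13 to 78 weeks, every change from week 48 onward stays negative. The largest rise at any time tabulated is 0.3 points, at week 24.

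**The case against.** The strongest reply is that the SAP has not abandoned the therapy rule. Its sentence ends by tying the censoring scan to the start of new therapy, an anchor that the protocol's own duration-of-response sentence lacks. SAP 1.1 says the plan is based on protocol section 10, so a condensed sentence should be read consistently with it: follow-up for response ends at the switch, as for PFS.

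Much of this stands. It would be wrong to say that the SAP discards the rule, or that it states that a later death is the event. For responders with no event it does cut off at new therapy, and the authors may well have intended the same for all. But the literal text makes the absence of an event the condition for censoring and does not confine events to the period before the switch. The PFS definition in the same section states the trigger that is missing here, which gives a programmer grounds to treat the two endpoints differently.

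A second reply is that few such deaths would be recorded. SAP 7.2.1 plans contact only at clinic visits, and the protocol sets no interval for survival follow-up. That is fair: the shares in simulation B assume that every cancer death up to cut-off is captured, so they are upper bounds for that scenario.

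A third reply is that SAP 7.6 plans no hypothesis test and the endpoint is secondary. This also stands, and it limits the importance of the point.

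**Conclusion.** The point holds as a departure from the protocol and an inconsistency within the SAP. The separate trigger is missing, and read literally the SAP lets a cancer death after a switch count as an event in a patient whom the protocol censors.

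A reader might infer that this credits the next drug's benefit to RAD001. The documents do not support that, and the calculations point the other way. An individual's recorded duration lengthens, but the patient also turns from a censored case into an event. In the scenarios run, the Kaplan-Meier curve falls by about 0.5 to 2 points at 48 weeks and 1.4 to 4.7 points at 84 weeks with the median unmoved (simulation B), or the median falls by 0.01 to 1.72 months (simulation A). No scenario raised the median.

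These sizes rest on assumed switching rates, survival after the switch and responder numbers, none of which the documents give. Only responders who switch without progression and later have a recorded cancer death (or, rarely, a recorded progression) are affected, on a descriptive secondary endpoint. PFS, response rate and overall survival are untouched. The correction is worth making because it removes a choice between two results at almost no cost.

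**What to change.** Replace the censoring sentence in SAP 7.2.1, Duration of Response, with wording such as:

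*Only disease progression or death due to the underlying cancer that occurs before the start of any new anticancer therapy counts as an event. A responder with no such event is censored at the last adequate tumor assessment before the earlier of the analysis cut-off and the start of new anticancer therapy.*

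This restores the protocol's trigger, keeps the SAP's clearer date anchor and matches PFS. It is better than pasting in the protocol sentence, which does not say which comes first, the event or the therapy.

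The cost is one sentence and the matching line of derivation code. Therapy start dates are already collected (Listing 16.4-2.1), so no new data are needed. If duration of response has already been programmed, check which reading was used and whether any responder is affected.
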